#### **5.3.1 Structured Interview:**

A structured one-on-one interview will occur with participants after completion of the HIIT program. The interview will be used to learn about barriers and concerns they experienced with regard to the current training protocol; preference of exercise mode and instruction; and opinions on what information participants would find helpful to improve the at-home training experience. While we do not intend to formally analyze the interview responses, we do anticipate that they will be useful for refining our intervention program for future trials.

- **5.3.2 Tolerability, Feasibility, Compliance, and Adherence:** Adherence and tolerability will be evaluated based on number of sessions attended/completed, modifications, such as change in mode, number of training days per week, and recovery days needed between sessions to complete training. The physical activity enjoyment scale will be given to assess participant enjoyment of exercise during the baseline and post-surgical testing visit.
- 5.3.3 To determine if HIIT decreases proliferation and induces apoptosis in the endometrial tumors, tissue microarrays (TMAs) will be constructed and immunohistochemical (IHC)analysis performed to assess Ki-67 staining (marker of proliferation) and caspase-3 expression (marker of apoptosis). The percentage of Ki-67 positive cells, termed the Ki-67 index, will be calculated pre- and post-treatment. Apoptosis will be evaluated by changes in activated caspase-3 expression. Individual slides will be digitized and analyzed using the Aperio ScanScope (Aperio Technologies, Vista, CA). This work will be performed with the expertise of the UNC-CH Translational Pathology Lab (TPL).
- **5.3.4** To test if HIIT alterations inhibits downstream targets of the insulin/IGF-1/AMPK/mTOR signaling pathway, IHC analyses of the ECs will be performed to determine expression of key targets of the insulin/IGF-1/mTOR pathway pre- and post-intervention, including p-IRS-1, p-IGF1R, p-AMPK, p-mTOR, p-Akt, p-S6, and p-4EBP-1.
- 5.3.5 To assess improvement in cardiorespiratory fitness with the HIIT intervention, peak oxygen consumption (VO2peak) will be measured preand post-HIIT. VO2peak is the gold standard for identifying fitness level and evaluating cardiovascular effects. This test will be used to establish individual training intensity. All participants will perform a ramp based cycling ergometer test with respiratory gases continuously monitored with open-circuit spirometry using a calibrated metabolic cart (True One 2400®, Parvo-Medics, Inc., Provo, UT). Data will be averaged over 15-second intervals, with the highest 15-sec oxygen consumption, minute ventilation, and heart

rate recorded as the peak oxygen consumption (VO2peak), time to exhaustion, and maximum heart rate, respectively.

- **5.3.6** To correlate improvement in obesity/overweight and insulin resistance with response to HIIT treatment, BMI, waist-to-hip ratio, body composition, HgBA1C, and diabetes status will be documented pre- and post-intervention. HgBA1C will be obtained pre-intervention only for all subjects. Body composition and visceral fat will be determined using portable ultrasonography as previously validated by our group. The Homeostasis Model Assessment Score [fasting insulin (microunits/ml) X fasting glucose (mmol/22.5)], a measurement of insulin resistance, will be calculated prior to and after the intervention.
- **5.3.7 To test if the metabolic profiles of blood and tumor correspond to HIIT responsiveness,** untargeted metabolomic/lipidomic analysis will be performed on (1) blood pre- and post- HIIT and (2) tumor pre- and post-HIIT intervention. Metabolic profiles of blood and tumor will be compared between pre- and post-intervention and the HIIT group. Untargeted metabolomic and lipidomic profiling will be performed using Ultrahigh Performance Liquid Chromatography-Tandem Mass Spectroscopy (UPLC-MS-MS) and Differential Mobility Spectroscopy-MS-MS (DMS-MS-MS). Urine is also being banked pre- and post-HIIT intervention for potential future metabolomic/lipidomic analysis.
- **5.3.8** Removal of Patients from Protocol Patients will be removed from the study if they indicate that they no longer wish to participate. Patients will be removed from study when any of the exclusion criteria listed in eligibility criteria apply.

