Potential prospective subjects will be seen in private clinic rooms by the physician and the team member that will be informing and consenting the subject. The purpose of this study and the risks and side effects of HIIT therapy will be addressed in the consent and verbally explained to the patients. The purpose of serum and tissue collection and the risk to these procedures will be verbally explained to the patients. Informed consent will be obtained from the patients by the study coordinator.

In order to ensure retention of subjects during the proposed HIIT intervention, subjects will be contacted weekly by study staff. These scheduled calls or text messages will ensure that the subjects have no questions about the intervention, that they are tolerating HIIT without any significant adverse effects, that they are syncing their Fitbits, and to make sure they are logging in their exercises on the website every time they work out. Furthermore, subjects will be provided multiple contact numbers for study personnel to contact with questions or concerns about the HIIT intervention (day or night).

After women have undergone hysterectomy/surgical staging for EC or CAH, their corresponding pre-treatment endometrial biopsies and post-treatment endometrial tissue/hysterectomy specimens will be obtained for comparison. Hysterectomy/tumor and repeat endometrial biopsy specimens from the EC and CAH patients in the operating room will be collected via the Tissue Procurement Core Facility (TPF) at the Lineberger Comprehensive Cancer Center (LCCC). In addition, the pre-operative endometrial biopsy slides and blocks will be obtained from referring physicians of these patients for analysis in this study. All patients would have had an endometrial biopsy performed prior to referral to the Gynecologic Oncology clinic as part of their diagnosis of endometrial cancer or complex atypical hyperplasia. Blood (10mL) and urine will be collected pre- and post-HIIT intervention for metabolomic profiling as a strategy to identify other potential biomarkers of response to HIIT. Fresh EC tissue will be collected post-HIIT intervention via hysterectomy for metabolomic profiling and correlation with metabolic changes in serum. These biospecimens will be stored indefinitely for research purposes unless the participant refuses to agree to storage for future use on the informed consent form.

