# CONFIDENTIAL UNIVERSITY OF NORTH CAROLINA

# 6.0 TIME AND EVENTS TABLE

# 6.1 Time and Events Table

	Pre-op or New visit	Baseline Testing Visit 	At home intervention 	Surgery	Post Surgical Testing Visit
	SOC appointment	During SOC appointment or at Applied Physiology Lab	4 to 8 Sessions	As scheduled per SOC	SOC appointment 2 to 4 wks post-surgery
Consent	X				
Eligibility Assessment	X				
Archival Tissue Retrieval	X				
Urine Sample	X			X	
Blood Sample	X			X	
Enrollment		X			
Waist and Hip Measurements		X			X
VO2peak		X			X3
Body Mass ultrasound		X			X
Visceral fat ultrasound		X			X
Fitbit Fitting		X			
Introduction to Fitness Plan		X			
Exercise Enjoyment Scale		X			X
Completion of Fitness plan			X		
Sync Fitbit data			X		
Participant Website Login			X		
Endometrial biopsy				X	
Hysterectomy Specimen				X	
Closing interview					X

Baseline visit can occur during SOC visit at time of consent and enrollment, or the subject will have the option to return to campus and perform visit at the exercise physiology lab at Fetzer Hall. If subject commits to return for baseline visit, but fails to return, the subject will not be enrolled on the study, and a new subject can be enrolled in that spot.

At home intervention begins with first HIIT session. During this time, subject will be called or texted by the study team to remind the subject to login to website, sync data, and troubleshoot technical difficulties.

The VO2 peak testing is optional at this visit.

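### Section 5.3.7 plans a pre- versus post-HIIT comparison of tumor metabolomics, but no pre-HIIT tumor is collected for it, and pairing archival with fresh tissue would confound HIIT with specimen handling

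*Combined protocol and SAP*

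**What the plan says.** Section 5.3.7 states that "untargeted metabolomic/lipidomic analysis will be performed on (1) blood pre- and post- HIIT and (2) tumor pre- and post-HIIT intervention". The item at issue is the second, "2) tumor pre- and post-HIIT intervention". The sentence after it sets the contrast: "Metabolic profiles of blood and tumor will be compared between pre- and post-intervention and the HIIT group". Both time points are therefore intended for tumor as well as for blood.

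Section 5.3 names one tumor collection for metabolomic work: "Fresh EC tissue will be collected post-HIIT intervention via hysterectomy for metabolomic profiling and correlation with metabolic changes in serum". For tissue from before HIIT it says that "the pre-operative endometrial biopsy slides and blocks will be obtained from referring physicians of these patients for analysis in this study", and it places that biopsy before the patient reaches the study clinic: "All patients would have had an endometrial biopsy performed prior to referral to the Gynecologic Oncology clinic". Footnote 1 of the schema in Section 5.1 likewise provides only for requesting the archival biopsy after consent.

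The Time and Events Table in Section 6.1 has one tissue row before HIIT, "Archival Tissue Retrieval", at the pre-operative visit. The rows for endometrial biopsy and hysterectomy specimen are marked at surgery only. Blood is marked at both the pre-operative visit and surgery.

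**The concern.** The analysis in Section 5.3.7 needs a tumor sample from before HIIT that is suitable for metabolomics and comparable with the sample taken after it. The collection sections provide no such sample. The analyst will then either find that the comparison cannot be run or fill the gap with the archival biopsy.

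The second course is the more harmful. Archival tissue and fresh hysterectomy tissue differ in preservation and in how they were obtained, and often in where. Section 5.1 predicts that HIIT will inhibit targets of the tumor's metabolic pathways. A shift produced by specimen handling could be read as support for that prediction. The protocol already recognises this kind of artefact: Section 5.3 adds a repeat biopsy at surgery so that specimen type is not mistaken for an effect of HIIT. It does not extend that safeguard explicitly to metabolomics.

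**Working it through.** The plan gives no figure to reproduce. The check is whether each planned comparison has the specimens it needs.

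| Material | Before HIIT | After HIIT | Source |
|---|---|---|---|
| Blood for metabolomics | Collected | Collected at surgery | 5.3, 6.1 |
| Tumor named for metabolomics | None | Fresh hysterectomy tissue | 5.3 |
| Diagnostic biopsy (office pipelle or D&C) | Archival slides and blocks, from the study center or a referring institution | Not applicable | 5.1, 5.3, 6.1 |
| Repeat pipelle biopsy | Not taken | Taken at surgery; preservation and any metabolomic use not stated | 5.3, 6.1, 7.1.3 |

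**Step 1.** Blood has both time points, so the first item of 5.3.7 is supported.

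**Step 2.** Tumor assigned to metabolomics exists after HIIT only. Fresh pre-HIIT tumor samples per patient: 0. Over the 20 evaluable patients planned in Section 8.1, that is 20 × 0 = 0, so no fresh-to-fresh paired difference can be formed for anyone.

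**Step 3.** Suppose the archival biopsy fills the gap. For one metabolite in patient i, write the paired difference as

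D(i) = h + a + e(i),

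where h is the change over the HIIT period, a is the average shift from preservation, specimen type and collecting site, and e(i) is noise with mean zero. The mean of D estimates h + a. Every HIIT patient goes from archival to fresh, so no contrast within the arm has a without h, and the two cannot be separated. The size of a is unknown: the documents give neither the fixative nor the assay's behaviour on blocks.

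**Step 4.** Two routes could reduce or cancel a.

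- *Matched pair.* Compare the archival biopsy with the repeat biopsy at surgery, processed the same way. Preservation is then matched and specimen type nearly so (a D&C diagnosis would still differ from a pipelle). Differences in site and in block age remain. The route requires an assay that runs on blocks.
- *Usual-care contrast.* If the 10 usual-care completers in Section 8.2 had the same archival and fresh specimens, the difference between arms would be (h + a) − (h₀ + a) = h − h₀, where h₀ is the change under usual care. This requires a to be the same in both arms and usual-care tumor to have been banked fresh. The documents confirm neither.

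Section 5.3.7 specifies neither route.

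**The case against.** The strongest reply is that the documents never say that archival tissue will be paired with fresh tissue. Section 5.3 provides a repeat biopsy at surgery for the very purpose of removing specimen-type differences, and that biopsy could be handled like the archival one. Section 8.2 also plans exploratory comparisons with 10 usual-care patients, in which a common handling shift would largely cancel. On this reading the plan merely fails to name its pre-HIIT specimen, in an analysis that serves hypothesis generation.

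Much of this stands, and it rules out several stronger claims that a reader might infer:

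- *That complete confounding is a documented fact.* It follows only if archival is paired with fresh. The plan does not state that pairing, although fresh hysterectomy tissue is the only tumor it assigns to metabolomics.
- *That no analysis could separate HIIT from handling.* That holds within the HIIT arm for the unmatched pair. A matched pair or a usual-care contrast could do better, if the specimens exist.
- *That a false-positive rate can be attached.* It would need a size for the handling shift and a specified test. The documents give neither, so any rate would only restate an assumption.
- *That Section 5.3 reserves the fresh tissue for a different purpose.* It names metabolomic profiling first and correlation with serum second. The problem is the missing pre-HIIT counterpart.

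What does not stand is the suggestion that the gap is harmless. No section directs the repeat biopsy to metabolomics or requires matched processing, so someone following the text has only fresh tissue after HIIT and archival tissue before it.

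**Conclusion.** The inconsistency is in the current text. Section 5.3.7 promises a tumor comparison for which Sections 5.1, 5.3 and 6.1 supply no comparable pre-HIIT specimen. As written, the comparison is either not feasible or, if archival tissue is set against fresh, not attributable to HIIT.

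The conclusion rests on one inference: that archival slides and blocks are preserved differently from tissue described as fresh. The documents do not name the fixative. The size of any resulting bias cannot be given.

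The reach is limited. Tumor metabolomics is not the primary endpoint in Section 3.1 and is not among the outcomes used for sample size in Section 8.2. The immunohistochemical endpoints, including Ki-67, do not depend on this fresh-tissue comparison, and the paired blood metabolomics has its samples. The point is worth acting on because it decides whether the trial can claim a within-patient metabolic change in the tumor, and correcting it costs little.

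**What to change.** Reconcile Sections 5.3, 5.3.7 and 6.1 in one of two ways.

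1. **Post-HIIT tumor only.** Remove the fresh-versus-archival tumor comparison from 5.3.7. Profile the fresh hysterectomy tissue and correlate it with serum metabolic change, as 5.3 already states. Correlation with Ki-67 change would be a sensible addition, since 5.3.7 aims to relate profiles to HIIT response, but the sentence in 5.3 names serum only.
2. **Matched pair.** If the assay can run on archival blocks, keep a paired comparison only between the archival biopsy and the repeat biopsy already taken at surgery, processed the same way. State the preservation method, and record collecting site and block age for each pair.

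Under either option, a comparison with usual-care hysterectomy tissue can be added if that tissue was banked fresh. Establish this before writing it in, and describe the comparison as small and exploratory. The sentence in 5.3.7 that sets the contrast needs rewriting anyway, because its closing words do not make clear what the HIIT group is compared with.

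The cost of option 1 is a text change with no new procedure; the trial then claims no within-patient metabolomic change in tumor. Option 2 keeps that claim but needs confirmation that the assay works on blocks, and some of the repeat biopsy must be set aside for it.

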# CONFIDENTIAL UNIVERSITY OF NORTH CAROLINA

# 6.0 TIME AND EVENTS TABLE

# 6.1 Time and Events Table

	Pre-op or New visit	Baseline Testing Visit 	At home intervention 	Surgery	Post Surgical Testing Visit
	SOC appointment	During SOC appointment or at Applied Physiology Lab	4 to 8 Sessions	As scheduled per SOC	SOC appointment 2 to 4 wks post-surgery
Consent	X				
Eligibility Assessment	X				
Archival Tissue Retrieval	X				
Urine Sample	X			X	
Blood Sample	X			X	
Enrollment		X			
Waist and Hip Measurements		X			X
VO2peak		X			X3
Body Mass ultrasound		X			X
Visceral fat ultrasound		X			X
Fitbit Fitting		X			
Introduction to Fitness Plan		X			
Exercise Enjoyment Scale		X			X
Completion of Fitness plan			X		
Sync Fitbit data			X		
Participant Website Login			X		
Endometrial biopsy				X	
Hysterectomy Specimen				X	
Closing interview					X

Baseline visit can occur during SOC visit at time of consent and enrollment, or the subject will have the option to return to campus and perform visit at the exercise physiology lab at Fetzer Hall. If subject commits to return for baseline visit, but fails to return, the subject will not be enrolled on the study, and a new subject can be enrolled in that spot.

At home intervention begins with first HIIT session. During this time, subject will be called or texted by the study team to remind the subject to login to website, sync data, and troubleshoot technical difficulties.

The VO2 peak testing is optional at this visit.

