# 5.2 Duration of Study

This study will last approximately 10 weeks total. During a SOC visit, subjects will be consented prior to hysterectomy. HIIT exercise will be a home-based program in the intervening weeks between SOC clinic visit and SOC surgery. Subjects can undergo baseline testing on the day of their SOC appointment in the North Carolina Cancer Hospital, or return to an exercise physiology lab in Fetzer Hall after their consent visit. All subjects will be directed to complete 4 to 8 sessions of the at home exercise program, log exercise in study website, and sync Fitbit data. At SOC surgery, endometrial biopsy and hysterectomy specimens will be collected. At a SOC post-operative appointment, 2 to 4 weeks post-surgery, post-testing will occur for all subjects.

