whether obtained at UNC-CH or at a referring institution, will be available for analysis in this study. The preferred treatment management for women with EC and CAH is surgical staging, which includes total hysterectomy, bilateral salpingo-oophorectomy, and lymph node assessment. Once enrolled on this pre-operative window study, patients will undergo baseline physiological testing to determine peak cardiorespiratory fitness (VO2peak) and maximum heart rate (HR). This physiological testing will then be used to construct an individualized HIIT intervention, consisting of 4 to 8 at-home training sessions, which will be completed prior to surgical staging. The effect of HIIT will be compared between pretreatment endometrial biopsies and their corresponding post-treatment hysterectomy specimens, with proliferation (i.e. Ki-67 staining) as the primary endpoint of interest. In addition, enrolled patients will undergo repeat endometrial biopsy post-HIIT intervention at the time of their surgical staging; this is being done to ensure that we are accurately evaluating the effects of the HIIT intervention on the endometrial tumors themselves and not differences found due to the type of specimen examined (i.e. endometrial biopsy specimen obtained in clinic versus hysterectomy specimen obtained at the time of surgery). Thus, we plan to compare pre-treatment endometrial biopsies to both post-treatment endometrial biopsies and hysterectomy specimens. Efficacy, tolerability, adherence, and exercise enjoyment will be assessed before and after the intervention as secondary outcomes. All women enrolled will receive a \$100 gift card for participating in this study.

[figure not shown]
Potential prospective subjects will be identified in the following ways: study staff may review the medical records of patients listed on the clinic schedule to determine if a patient meets eligibility criteria for this research study prior to the patient meeting with the physician. Alternatively, patients may be referred to the research team by their UNC physician, outside physician, self-refer or may be discussed at disease specific conferences. In all cases, a member of the research team will review the medical record to see if the patient meets basic eligibility criteria. The patient's physician will present options to the patient and, if the patient is interested, the research study coordinator will consent the patient and HIPAA authorization will be sought.

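### Waist-to-hip ratio, body composition and exercise enjoyment are presented as post-intervention values but measured only 2 to 4 weeks after hysterectomy, so a within-arm change cannot be separated from surgery and recovery

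*Combined protocol and SAP*

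**What the plan says.** Section 5.3.6 states its aim as "To correlate improvement in obesity/overweight and insulin resistance with response to HIIT treatment". For this, "BMI, waist-to-hip ratio, body composition, HgBA1C, and diabetes status will be documented pre- and post-intervention". The same paragraph adds that "Body composition and visceral fat will be determined using portable ultrasonography as previously validated by our group", with no separate timing for visceral fat.

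Section 5.3 says of the secondary outcomes: "Efficacy, tolerability, adherence, and exercise enjoyment will be assessed before and after the intervention as secondary outcomes". Section 5.3.2 is more specific about enjoyment: the scale "will be given to assess participant enjoyment of exercise during the baseline and post-surgical testing visit".

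The schedule is in two places. In the Section 6.1 table, the rows for "Waist and Hip Measurements", the two ultrasound assessments and the enjoyment scale are each marked twice: at the baseline testing visit and in the column headed "SOC appointment 2 to 4 wks post-surgery". Section 5.2 agrees: "At a SOC post-operative appointment, 2 to 4 weeks post-surgery, post-testing will occur for all subjects".

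**The concern.** The label and the schedule point to different moments. A reader of Section 5.3.6 would take the second waist-to-hip and body-composition values as the state at the end of HIIT. By the schedule they are taken after total hysterectomy, removal of tubes and ovaries and lymph node assessment (the surgery described in Section 5.3), and after 2 to 4 weeks of recovery.

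The attribution is at stake. Section 5.1 predicts, in a paragraph about the effects of HIIT, that BMI and waist-to-hip ratio will fall. Section 5.3.6 then relates improvement in such measures to HIIT response. The study now has a single arm, so a change over this interval could be reported as a HIIT effect when part or all of it came from the operation or the recovery. A surgical effect in the other direction could hide a real HIIT effect.

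**Working it through.** The plan has no figure to reproduce here, so the check sets the timings side by side.

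1. **Intervention.** Sections 5.1 and 8.1: 4 to 8 sessions, about 2 to 3 weeks, finished before surgery.
2. **Specimens.** Section 6.1 schedules the second blood and urine samples, the repeat biopsy and the hysterectomy specimen on the day of surgery. These are the values that Sections 5.3 and 5.3.7 treat as post-HIIT, and they come before recovery begins.
3. **The measures at issue.** Waist and hip, body-composition and visceral-fat ultrasound and enjoyment: baseline, then 2 to 4 weeks after surgery. None is marked in the surgery column or during the home intervention. BMI is named in Section 5.3.6 but has no row of its own in Section 6.1, so its timing cannot be checked there.
4. **Gap.** The last session comes before surgery, so the second value lies at least 2 to 4 weeks after it. That is about as long as the intervention itself, with a major operation in between.

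The terms for after HIIT therefore cover two time points: day of surgery for specimens, and 2 to 4 weeks later for body measures and enjoyment. For the latter,

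observed change = HIIT effect + surgery and recovery effect + effect of time since the last session.

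One pre-post difference cannot identify three terms.

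**Illustration of consequence.** The documents give no surgical effect on these measures, so its size is an assumption, shown over a range. Inputs: n = 20 (the evaluable target in Section 8.2), normally distributed changes, true HIIT effect zero, surgical shift s in units of the SD of the change, exact Wilcoxon signed-rank test at two-sided 0.05, 20,000 simulated trials. The plan names this test for Ki-67 and VO2peak; its use for these measures is assumed.

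| Assumed shift s (SD) | Chance of a significant change with no HIIT effect |
|---|---|
| 0 | 5% |
| 0.1 | 7% |
| 0.25 | 18% |
| 0.5 | 54% |
| 0.75 | 87% |
| 1.0 | 99% |

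The simulation error is at most √(0.5 × 0.5 / 20,000) = 0.0035, or about 0.4 percentage points.

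**The case against.** The case on the other side has several parts.

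**The timing is disclosed.** Sections 5.2 and 6.1 and a schema footnote in Section 5.1 state it, and a value taken after surgery is literally after the intervention. This stands as far as it goes. Section 5.3.2 is open about enjoyment, so the only loose label for that measure is in Section 5.3. Visceral fat is not itself called post-intervention; it is drawn in by its place in Section 5.3.6. But disclosure of the visit date does not support relating the change to HIIT response.

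**There are controls.** Section 8.2 keeps an exploratory ANCOVA against 10 randomized usual-care completers and extends it to other variables. These patients also had surgery planned, so the comparison can remove part of the surgical effect. This stands in part. Ten is few, and HIIT patients enrolled after the design change were not randomized. The amendment summaries, apparently newest first, suggest that the BMI floor fell from 30 to 25 after the change to one arm, so later HIIT patients may differ from the controls on these very measures.

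**Enjoyment is a questionnaire.** Surgery does not alter it as it may alter a waist measurement. This stands: the second value is a delayed report, possibly coloured by recovery, and it is the weakest of the measures in this point.

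**Stronger readings are tempting.** A reader might infer that the values reflect surgery rather than HIIT. The documents give neither size nor direction for a surgical effect, so only inseparability is supported. A reader might compute that 2/(3+2) = 40% to 4/(2+4) = 67% of the time from first session to second value is post-surgical. That is a calendar share, not a measure of bias, and it assumes that surgery follows the last session at once. A reader might also take HIIT response to mean the Ki-67 change; Section 5.3.6 does not define it, and our copy shows no text under Section 2.2.

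**Conclusion.** The point holds in a limited form. For waist-to-hip ratio, body composition, visceral fat (by its place in Section 5.3.6) and enjoyment, the only post-baseline value comes 2 to 4 weeks after hysterectomy. A within-arm change in them cannot be credited to HIIT.

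The size of the distortion is unknown. Under the assumed shifts above, the chance of a spurious finding runs from the nominal 5% to 99%, and it already exceeds half at 0.5 SD. This shows sensitivity and is not an estimate of bias.

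These are secondary or exploratory measures. Ki-67 and the blood, urine and tissue analyses rest on day-of-surgery samples and do not share the problem. VO2peak does share the post-surgical timing; it is optional at that visit yet still named in the primary analysis, and it deserves separate attention.

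Reading the measures through the control comparison assumes that the usual-care completers attended the same post-surgical visit. The current text no longer sets out the control schedule, so this should be confirmed from the study records.

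**What to change.** In Sections 5.3 and 5.3.6, relabel these second values as *post-surgical (2–4 weeks after surgery)* to match Section 6.1. State that their within-arm change will not be attributed to HIIT, nor correlated with HIIT response as a post-HIIT effect. Interpret them only through the exploratory ANCOVA against the usual-care completers, and state its limits: 10 controls, and later HIIT patients not randomized.

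Optionally, for remaining patients, add a time point between the last session and surgery. The enjoyment scale could go out through the study website or by email; Section 4.1 already requires smartphone and email access. Waist, hip and weight could be taken pre-operatively where staff are already present. This value should be additional and should not replace the post-surgical one. Replacing it would lose the control comparison for these measures, because the completed controls have no pre-surgical value.

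**Cost.** The relabelling costs only wording and works for patients already finished. The price is that the plan claims less about HIIT for these measures. The optional time point is not free: Section 7.1.2 places the second blood draw under general anesthesia and the schema places the biopsy after sedation, so no research contact with an awake patient is documented that day, and pre-operative measurements elsewhere would need staff time. Finished patients would lack the added value.
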